5.11.3. Missing/Partial Dates for Multiple Sclerosis Symptom Onset and Diagnosis Date

Multiple sclerosis symptom onset dates and diagnosis dates that are partially missing will be imputed as follows:

- If year is present, but month and day are missing, impute to July 1
- If year and month are present but day is missing, impute to 1st of month
- If year and day are present but month is missing, impute to July
- If year is missing, or date is completely missing – do not impute. Leave as missing

5.11.4. Multiple Sclerosis Walking Scale Imputations

A maximum of three missing items in the twelve-item scale will be allowed. As necessary, any missing value will be imputed as the average of the non-missing items. If more than three of the twelve items have missing responses, no total score will be computed for the given timepoint.

5.11.5. Laboratory Data Imputations

If a lab value is reported using a non-numeric qualifier (e.g., less than [<] a certain value, or greater than [>] a certain value), the given numeric value will be used in the summary statistics, ignoring the non-numeric qualifier. For instance, a value reported as “<200” would be listed as such, but summarized as “200.”

5.12. Software Details

All statistical procedures will be performed using SAS[®] Version 9.3 or higher.

5.13. Reporting Conventions

All tables, listings, figures and any other supportive SAS output will include in the footer explanatory notes that will indicate, at a minimum, the programming source (i.e., name, file path of the SAS program that generates the output), data extraction date, and run date.

Continuous data will be described using descriptive statistics as follows: number of observations (n), mean, median, standard deviation, minimum, and maximum, unless otherwise specified. All minimum and maximum values will be displayed with the same number of decimal places relative to the raw data, the mean and median will be displayed with one additional decimal place, and the standard deviation will be displayed with two additional decimal places.

Categorical data will be summarized by the number and percentage of subjects in each category. The denominator of all percentages will be number of subjects in the population of interest, unless otherwise stated. When count data are presented, the percent will be suppressed when the count is zero in order to draw attention to the non-zero counts. A row denoted "Missing" will be included in count tabulations where necessary to account for dropouts and missing values. Non-zero percentages will be rounded to one decimal place, except 100% will be displayed without any decimal places.

In summary tables for categorical data, all categories will be presented if they are specified on the Case Report Form (CRF), or if categories are ordered intervals (e.g., age groups), regardless of whether data were present in each category, unless otherwise specified. For other categorical data (e.g., AEs and medications), only categories with non-zero frequencies will be presented.

P-values will be rounded to 4 decimal places. P-values that round to 0.0000 will be presented as '<0.0001' and p-values that round to 1.000 will be presented as '>0.9999'. Confidence intervals (CIs) will be presented as 2-sided 95% CIs unless specified differently in specific analysis.

Data will be displayed in all listings sorted by treatment, study site, and subject number concatenated with site number. All summaries will be presented by treatment group, unless otherwise specified.

When no data are available for a table or appendix, an empty page with the title will be produced with suitable text (e.g., "There are no observations for this table/appendix.").

6. Subject Disposition

6.1. Disposition

The all enrolled set will be utilized for a table summarizing the number of subjects included and excluded from each analysis set, along with reasons for exclusion. The summary will be provided by treatment group and overall and will also be provided in a data listing.

The ITT set will be utilized for a table summarizing subjects discontinuing study drug early by treatment group and overall and will include the following information:

- Whether the subject completed treatment through Week 16 (Yes, No)
- As applicable, the reason for premature study drug discontinuation

The ITT set will be utilized for a table summarizing subject study completion status by treatment group and overall and will include the following information:

- Subject completion status (Yes, No)
- Whether the subject consented to participate in the open label extension (Yes, No)
- Reason for early termination

All disposition information will also be provided in data listings.

6.2. Protocol Deviations

Protocol deviations will be recorded within the PPD Clinical Trial Management System (CTMS) and undergo cross-functional team review prior to database lock in order to finalize the PP set. The Deviation Guidance Document contains all potential protocol deviations classified by CTMS subtype. After review, deviations deemed to be of special interest will be classified as significant protocol deviations.

Major protocol deviations are those deviations that may have an impact on the efficacy analysis or the safety of the subject. Major protocol deviations can be related to study inclusion/exclusion criteria, trial conduct, patient management, or patient assessments. Major protocol deviations will be determined by the sponsor and submitted to PPD prior to database lock. Major protocol deviations are a subset of significant deviations.

The number and percentage of subjects with significant protocol deviations will be summarized by treatment group and overall using the ITT set. Subjects will be counted once within each deviation category regardless of how many deviations they have in that category.

All significant protocol deviations will also be provided in a data listing.

A blinded review of the data listings will be conducted prior to database lock to determine the extent to which subjects completed the study according to the protocol. In the event that the blinded data review reveals major protocol deviations that impact interpretation of efficacy assessments, the per-protocol (PP) analysis set may exclude additional subjects. Final decisions regarding subjects to be included in all analysis sets will be made prior to any unblinding of the treatment allocations and database lock.

7. Demographics and Baseline Characteristics

7.1. Demographics

The following demographic information will be summarized for the Safety, ITT, and PP sets by treatment group and overall:

- Age (years), calculated as (informed consent date – birth date + 1) / 365.25
 - No rounding will be performed and only the integer value will be retained
- Categorical Age (<55, ≥55, <65, ≥65)
- Gender (Female, Male)
- Ethnicity (Hispanic or Latino, Not Hispanic and Not Latino)

- Race (White, African American, Asian, American Indian or Alaska Native, Native Hawaiian or Other Pacific Islander, Other)
- Height (cm)
- Weight (kg)
- BMI (kg/m²)
- Categorical BMI (Underweight (<18.5), Normal (18.5 - <25), Overweight (25 - <30), Obese (≥30))
- Expanded Disability Status Scale (EDSS) score at Baseline
- Baseline T25FW (<26.5 s, ≥26.5 s)

Demographic information will also be provided via data listings.

7.2. Medical History

7.2.1. General Medical History

General medical history information will be summarized using the ITT set by system organ class.

MedDRA dictionary Version 21.0 will be used for reporting and will be described in the relevant table and listing footnotes.

General medical history information will also be provided via data listings.

7.2.2. Multiple Sclerosis Disease History

The following multiple sclerosis specific disease information will be summarized for the ITT set by treatment group and overall:

- Type of Multiple Sclerosis (Relapsing Remitting, Secondary Progressive, Progressive with Relapse, Progressive Without Relapse)
- Time Since Symptom Onset (years), calculated as (informed consent date – date + 1) / 365.25
- Time Since Diagnosis (years), calculated as (informed consent date – date + 1) / 365.25
- Corticosteroids (IV or Oral) or ACTHAR Gel Use within 30 days prior to screening (Yes, No)
- Prior Amantadine Use (Yes, No)
- Prior Dalfampridine Use (Yes, No) and Form (Ampyra/Fampyra, 4-Aminopyrimidine, 2-4-Diaminopyrimidine) and reason for stopping (Side Effects, Loss of Efficacy, No Efficacy, Other)

Multiple sclerosis disease history will also be provided via data listings.

7.3. Inclusion and Exclusion Criteria

Inclusion and exclusion violations will be provided via data listings.

8. Treatments and Medications

8.1. Prior and Concomitant Medications

Prior medications are defined as medications with a stop date occurring from 30 days prior to the screening visit up to the day prior to randomization. Concomitant medications are defined as medications taken on or after the date of randomization through the date of last dose of study drug (inclusive) or listed as ongoing. Medications with start and stop dates (or ongoing) which bracket the randomization date will be summarized as both prior and concomitant medications.

All non-study drugs (including prescribed and over the counter medications) taken during the study will be collected on the CRF. All medications will be coded according to the World Health Organization (WHO) Drug Dictionary and summarized using the Anatomical Therapeutic Chemical (ATC) class (Level 2) and preferred term (PT). The WHO Drug Dictionary dated March, 2018 will be used for study reporting and will be detailed in the relevant table and listing footnotes.

Prior medications will be summarized for the Safety set. Medications taken prior to enrollment and prior to randomization will be summarized separately. At each level of summarization, a subject is counted once if he/she reported one or more medications at that level.

Concomitant medications will be recorded beginning with the first dose of study drug and continuing through the last study visit. Concomitant medications will be summarized for the Safety set. At each level of summarization, a subject is counted once if he/she reported one or more medications at that level.

Prior and concomitant medication information will also be provided via data listings.

8.2. Study Treatments

Study drug will be packaged in child-resistant blister wallets, each containing a total of 36 capsules (two capsules per dose, allowing for a two-week supply plus two extra doses per week).

Table 1: Expected Capsules Dispensed and Returned by Visit

Visit	Expected Capsules Dispensed at The Indicated Visit	Expected Capsules Returned at The Next Visit
Week 0	72	16*
Week 2	N/A	N/A
Week 4	36	8
Week 6	36	8
Week 8	72	16
Week 12	72	16
Week 16	0	N/A

* 2 blister wallets containing 36 capsules each are dispensed at Week 0. One is to be collected at Week 2, the other at Week 4

8.2.1. Extent of Exposure

The extent of double-blind study drug exposure will be summarized for the active treatment arms with continuous measures (n, mean, median, standard deviation, minimum, and maximum) and categorical measures (1-7 days, 8-14 days, 15-28 days, 29-56 days, 57-84 days, and >84 days; >= 1 month, >=2 months, and >=3 months) using the Safety set.

Extent of exposure will be calculated as follows:

$$\begin{aligned} & \textit{Extent of exposure (days)} \\ &= (\textit{Date of Last Dose of Double Blind Study Drug} \\ & - \textit{Date of First Dose of Double Blind Study Drug}) + 1 \end{aligned}$$

Study drug exposure details for both the Placebo Run-in and Double-Blind Treatment periods will also be provided via data listings.

8.2.2. Drug Accountability and Treatment Compliance

Treatment compliance in the Placebo Run-In and Double-Blind Treatment Periods will be summarized separately for the Safety set and calculated as follows:

$$\textit{Treatment compliance (capsules, \%)} = \left(\frac{A}{P} \right) * 100$$

where

P = The number of capsules prescribed = Number of days dosing expected * 2 Capsules

A = The actual number of capsules taken

Total number of capsules prescribed will be calculated based on the number of capsules prescribed from Day 1 to the last day of dosing. If the number of capsules returned at a given visit is missing, overall treatment compliance will be missing. Non-compliance is defined as less than 80% or more than 120% non-missing compliance with study drug. Subjects with missing compliance are classified as non-assessable.

Drug accountability and treatment compliance data will also be provided via data listings.

9. Efficacy Analysis

The ITT set will be used for the primary efficacy analysis, as well as for the primary analysis of each secondary endpoint.

9.1. Primary Efficacy Analysis

The primary efficacy endpoint is the proportion of responders in each treatment group as defined in [Section 3.2.1](#).

The objective of the primary efficacy analysis is to compare the 274 mg ADS-5102 group versus the placebo group in terms of the difference (active minus placebo) in the proportion of responders at Week 16 using the ITT analysis set. The Farrington-Manning test will be used to obtain a 2-sided p-value based on the resulting Z-score. The Miettinen-Nurminen (MN) approach will be used to obtain the 95% confidence interval (CI) for the difference. Superiority will be concluded if the 2-sided p-value is less than 0.05 and the lower limit of the 2-sided 95% CI is greater than 0.00. (Note that this test is effectively a one-sided test at the 0.025 level.)

This test can be expressed mathematically as follows:

$$H_0: d = 0$$
$$H_1: d > 0$$

Where $d = p_1 - p_0$ (i.e. risk difference between the proportion of responders in the 274 mg ADS-5102 group and the proportion of responders in the placebo group).

The primary efficacy analysis will be provided via a summary table.

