10. ASSESSMENT OF EFFICACY

Evaluations relating to efficacy to be performed during the study are described in the following table. Full details on how efficacy assessments are to be performed will be provided in the study manual.

Table 4: Efficacy Assessments

Assessment	Study Visit	Description
Timed 25-Foot Walk (T25FW)	Screening Week 0, Week 2 Baseline/Week 4 Week 8 Week 12 Week 16 (or ET) Safety Follow-Up	The T25FW is a measure of lower extremity function. The subject is directed to a clearly marked 25-foot course and is instructed to walk 25 feet as quickly as possible, but safely. The task is immediately administered again by having the subject walk back the same distance. The result is reported as time to complete (seconds) or speed (feet per second). Improvement is indicated by a decrease in time or an increase in speed.
Timed Up and Go (TUG)	Week 0, Week 2 Baseline/Week 4 Week 8 Week 12 Week 16 (or ET) Safety Follow-Up	The TUG is a measure of lower extremity strength, balance, and coordination. The subject stands up from a chair, walks 3 meters then turns around and walks back to the chair to sit down. The result is reported in seconds. Improvement is indicated by negative change scores.
2-Minute Walk Test (2MWT)	Week 0, Week 2 Baseline/Week 4 Week 8 Week 12 Week 16 (or ET) Safety Follow-Up	The 2MWT is a measure of lower extremity function. The subject is instructed to walk as far as possible in 2 minutes, and the distance is measured in meters. Improvement is indicated by positive change scores.
Multiple Sclerosis Walking Scale-12 (MSWS-12)	Week 0, Week 2 Baseline/Week 4 Week 8 Week 12 Week 16 (or ET) Safety Follow-Up	The MSWS-12 is a 12-item walking scale that is a measure of subject-reported walking ability during the past 2 weeks. Each item is scored on a 1 to 5 scale. A total score can be generated and transformed to a 0 to 100 scale. Improvement is indicated by negative change scores.

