5.1. Randomization, Stratification, and Blinding

A subject is considered randomized at Baseline/Week 4, when the site confirms the randomization event via a centralized randomization system (interactive web response system [IWRS]).

Following completion of the 4-week Single-Blind Placebo Run-in Period, consented subjects who continue to meet eligibility criteria will be randomly assigned in equal probability to 1 of 3 treatment groups: placebo, 137 mg ADS-5102, or 274 mg ADS 5102. No stratifications are being utilized in the randomization design.

The identity of the treatment assigned to individual subjects can be revealed in an emergency only. A subject's treatment assignment should only be unblinded when knowledge of treatment is essential for the safety of the subject. Emergency unblinding will be considered a major protocol deviation.

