5.2. Sample Size

Based on the results from the Phase 2 study, responder rates of 24% and 33% were observed at Week 4 for subjects treated with placebo and 274 mg ADS-5102, respectively, in the modified intent-to-treat (MITT) analysis set. In the present study, it is anticipated that the placebo response rate at Week 16 will be no greater than 20% and the response rate among subjects treated with 274 mg or 137 mg ADS-5102 will be at least 33%. Using these estimates, 180 randomized subjects per active treatment group and placebo group will be needed for the test of differences in proportions (Farrington-Manning approach for the Miettinen-Nurminen [MN] test) to have 80% power at the 2-sided 5% significance level to detect this 13% difference favoring ADS-5102. Assuming a 5% dropout rate during the 4-week Single-Blind Placebo Run-In Period, 570 subjects will be enrolled in the study to randomize 540.

For this sample size of 180 randomized subjects per group, power will be at least 80% to detect treatment differences (ADS-5102 versus placebo) of -2.7 seconds and 5.0 meters in the changes from baseline at Week 16 in the TUG test and 2MWT when the standard deviations of the

change from baseline are no greater than 6.0 sec and 14.9 meters, respectively, and the dropout rate is not greater than 20%.

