9.2. Key Secondary Efficacy Analyses

The key secondary endpoints are the mean changes from Baseline between treatment groups at Week 16 for the T25FW (feet/second), TUG (s), and 2MWT (m). These are described in [Section 3.2.2.1](#).

Provided superiority of 274 mg ADS-5102 versus placebo is shown in the primary analysis, the key secondary objectives will be evaluated using a fixed-sequence gatekeeping strategy to control the overall Type I error rate at 5%. Using this approach, the following research hypotheses will be evaluated sequentially in the order given using the ITT analysis set:

1. Superiority of 274mg ADS-5102 compared to placebo in mean change from baseline at Week 16 in the T25FW(feet/second) test

2. Superiority of 274 mg ADS-5102 compared to placebo in mean change from baseline at Week 16 in the TUG (s) test
3. Superiority of 274 mg ADS-5102 compared to placebo in mean change from baseline at Week 16 in the 2MWT (m)
4. Superiority of 137 mg ADS-5102 compared to placebo in terms of the proportion of T25FW responders at Week 16
5. Superiority of 137 mg ADS-5102 compared to placebo in mean change from baseline at Week 16 in the T25FW (feet/second) test
6. Superiority of 137 mg ADS-5102 (s) compared to placebo in mean change from baseline at Week 16 in the TUG test
7. Superiority of 137 mg ADS-5102 compared to placebo in mean change from baseline at Week 16 in the 2MWT(m)

At each step, superiority will be concluded if the 2-sided p-value is less than 0.05 and the lower limit of the 2-sided 95% CI is greater than 0.00, for tests comparing responder rates or mean changes from baseline in 2MWT and T25FW, or the 2-sided 95% CI is less than 0.00, for tests comparing mean changes from baseline in the TUG. If a non-significant result (p-value ≥ 0.05) or a p-value < 0.05 is noted but superiority is not shown, no further inferential conclusions will be drawn and any subsequent statistically significant result will be declared supportive of efficacy only. This strategy effectively controls the Type I error rate at the 2.5% level (one-sided) for testing superiority of ADS-5102 versus placebo.

The statistical test of difference between 137 mg ADS-5102 versus placebo in terms of responders at Week 16 (Item 4 above) will be done using the same approach used for the primary analysis.

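### The primary responder test and the 137 mg responder test adjust for no pre-randomization covariate; using the T25FW speeds already collected could add roughly 0 to 4 points of power

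*Combined protocol and SAP*

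**What the plan says.** SAP 9.1 defines the target as d = p1 - p0, the difference in Week 16 responder proportions between 274 mg and placebo. It states: "The Farrington-Manning test will be used to obtain a 2-sided p-value based on the resulting Z-score". The 95% interval is Miettinen-Nurminen, and superiority needs both p < 0.05 and a lower limit above zero. Protocol 14.4.1 describes the same crude comparison. In SAP 9.2 the step 4 test of 137 mg responders "will be done using the same approach used for the" primary analysis.

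The design does not balance on any prognostic factor either: "No stratifications are being utilized in the randomization design" (SAP 5.1).

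Table 4 in protocol section 10 schedules T25FW at "Screening Week 0, Week 2 Baseline/Week 4 Week 8 Week 12" and later visits, and randomization takes place at Week 4. SAP 5.4 makes Baseline the mean of the Week 2 and Week 4 visit averages, each from up to two walks. (Protocol 14.4.1 names Weeks 0 and 2; SAP section 11 describes a renumbering of weeks. The SAP definition is used here.) Screening speed serves eligibility. Week 0 speed would enter the endpoint only through the fallback rule for missing Baseline visits.

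The sensitivity analyses in SAP 9.1.1 repeat the crude test in per-protocol subjects and in completers. SAP 9.1.2 uses baseline variables only to form subgroups. No adjusted responder analysis is planned. The key secondary MMRMs in SAP 9.2 do include the baseline value as a covariate.

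**The concern.** A responder must be at least 20% faster than his or her own Baseline. A subject whose Week 2 and Week 4 walks were slow by chance crosses that line more easily, and one whose walks were fast by chance less easily. Part of the variation in responder status is therefore predictable before randomization. The Screening and Week 0 walks carry that information, because they show whether Baseline was unusual for the subject. The crude test leaves this predictable variation in its standard error.

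What is at stake is efficiency. The primary test opens the gate to all seven key secondary hypotheses, and the sample size leaves almost no margin over 80% at the planning rates. A standardized risk difference estimates the same d with a somewhat smaller variance.

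**Working it through.** **1. Inputs from SAP 5.2.** Placebo: "it is anticipated that the placebo response rate at Week 16 will be no greater than 20"%. Active: "the response rate among subjects treated with 274 mg or 137 mg ADS-5102 will be at least 33"%. Size: "180 randomized subjects per active treatment group and placebo group will be needed". Target: "to have 80% power at the 2-sided 5% significance level to detect this 13% difference favoring ADS-5102".

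**2. Reproduce the stated power.** With pooled rate (0.20 + 0.33)/2 = 0.265:

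- SE under the null = sqrt(0.265 × 0.735 × 2/180) = 0.04652
- SE under the alternative = sqrt((0.20 × 0.80 + 0.33 × 0.67)/180) = 0.04601
- Power = Φ((0.13 - 1.96 × 0.04652)/0.04601) = Φ(0.844) = 80.06%

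Solving for n gives 180 per arm. Exact enumeration gives 80.5% for Farrington-Manning and 80.1% with the Miettinen-Nurminen N-1 factor. The plan's figure stands.

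**3. Effect of adjustment.** If pre-randomization covariates explain a share R² of the variance of responder status, both standard errors shrink by about sqrt(1 - R²). The equivalent size is 180/(1 - R²). For example, at R² = 0.05 the factor is 0.9747, and power = Φ((0.13 - 1.96 × 0.04534)/0.04485) = Φ(0.917) = 82.05%.

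| R² | Power | Gain (points) | Equivalent n per arm |
|---|---|---|---|
| 0 | 80.1% | 0 | 180 |
| 0.02 | 80.8% | 0.8 | 184 |
| 0.05 | 82.0% | 2.0 | 189 |
| 0.08 | 83.3% | 3.2 | 196 |
| 0.10 | 84.0% | 4.0 | 200 |

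A gain of 3 to 4 points needs R² of about 0.075 to 0.100.

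**4. Plausible R².** The documents give no R², correlation or visit-to-visit SD for T25FW speed, so these are assumptions. Log speed was simulated with between-subject SD 0.40 and 400,000 subjects per setting. The SD of change was set to put about 20% of placebo subjects beyond ln(1.2): with nobody missing, 0.1823/0.8416 = 0.217. That change was split between visit-to-visit noise and lasting subject-level change. If all of it is noise, the visit SD is 0.217/sqrt(1.5) = 0.177, because Baseline averages two visits. Missing Week 16 counted as non-response. R² was averaged over the two arms and put into the formula of step 3. Gains in points from adjusting for Screening, Week 0 and Baseline speed:

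| Noise share of change variance | R², none missing | Gain, none missing | Gain, 10% missing | Gain, 20% missing |
|---|---|---|---|---|
| 100% | 0.098 | 3.9 | 3.5 | 3.1 |
| 75% | 0.072 | 2.9 | 2.5 | 2.3 |
| 50% | 0.048 | 1.9 | 1.6 | 1.5 |
| 25% | 0.023 | 0.9 | 0.8 | 0.7 |
| 10% | 0.009 | 0.3 | 0.3 | 0.3 |

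Adjusting for Baseline alone gave R² of at most 0.020, a gain of 0 to 0.8 points.

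**5. Full-trial simulation.** One set had 180 per arm, entry limited to 8-45 s, visit SD 0.12-0.15, SD of true change 0-0.17, 0% or 20% missing, and 4,000 trials per scenario. The crude test had 80.1-81.7% power. Baseline-only adjustment added 0-0.5 points. Adding Screening and Week 0 added 0.6-3.6 points and cut the variance of the risk difference by about 2-7%. One-sided type I error was 2.2-2.8% adjusted and 2.1-2.8% crude (Monte Carlo SE about 0.25 points). Another set gave gains of about 0 to 4 points, variance lower by 1-9%, about 2 points of gain with 20% missing, and type I error of 2.6-2.9% adjusted against 2.7-2.8% crude.

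**The case against.** The strongest reply is that nothing in the plan is wrong. The crude test is valid and easy to explain, estimates the stated risk difference and delivers the stated power. The planning rates are worded as bounds, so 80% is a floor if they hold. All of that stands.

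Four stronger readings are tempting, and the documents do not support them:

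- A reader might infer that the test ignores pre-treatment data altogether. It does not. Up to four pre-randomization walks per subject form Baseline, and that averaging already reduces the error described above. What is missing is covariate adjustment and, normally, the Screening and Week 0 speeds.
- A reader might take 3 to 4 points as the expected gain. That is the top of the range. It needs change to be mostly short-term noise and little dropout. Lasting subject-level change over 12 weeks is plausible in MS and shrinks the gain. So does missing data counted as non-response, and SAP 5.2 allows up to 20% dropout for the continuous endpoints.
- A reader might argue that matching the MMRMs is reason enough. They adjust for Baseline only, and doing the same here gains almost nothing.
- A reader might call the change free. It needs no subjects or visits, but it does need pre-specified modelling and edits in several places. A logistic model could also be unstable in the small subgroups of SAP 9.1.2.

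These points limit the size of the benefit. They do not remove it: the adjusted analysis is valid, keeps the same estimand and is somewhat more efficient.

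**Conclusion.** The point holds as a modest missed efficiency. The primary and step 4 responder tests use no pre-randomization covariate, and no adjusted analysis is planned even as a sensitivity analysis. Adjusting for Baseline, Week 0 and Screening speed would raise power from 80.06% by roughly 0 to 4 points.

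The fact that the tests are unadjusted comes straight from the documents. The size of the gain does not. It rests on an assumed between-subject SD of 0.40 on log speed, an assumed split of change between visit noise and lasting change, and assumed missingness of 0 to 20%. No finding of invalidity or of a shortfall against the stated power follows.

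**What to change.** Before unblinding, make the primary and step 4 estimate a covariate-standardized risk difference:

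- Fit a logistic model with arm, log Baseline speed, log Week 0 speed and log Screening speed. Assistive-device use is optional; its contribution was not simulated.
- Average the predicted responder probabilities over all ITT subjects under each arm and take the difference. State whether the model is fitted to all three arms or to the compared pair. Do not report a conditional odds ratio instead, because that would change the estimand.
- Use an influence-function standard error, a 2-sided 5% test and the matching 95% interval.
- Keep missing Week 16 as non-response. Replace a missing covariate by its overall mean, blind to arm.
- Keep the crude Farrington-Manning/Miettinen-Nurminen result as a sensitivity analysis, and keep the crude method for the subgroups in SAP 9.1.2.

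The cost is text and programming. The method wording changes in the synopsis, protocol 14.4.1 and SAP 9.1, and step 4 follows by its cross-reference. Protocol 14.1 and SAP 5.2 should note that the sample size is based on the crude test. The downside is that the primary p-value becomes model-assisted, and the model and variance estimator must be fixed in advance. If the sponsor prefers to keep the crude test as primary, the adjusted analysis could at least be added to SAP 9.1.1 as a sensitivity analysis, though that would not raise the power of the gatekeeping test.
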